### **Impact of Impending and Actual Pathological Fractures on Reduction of Pain**

Pain reduction following prophylactic fixation of impending pathological fractures and fixation of fractures secondary to metastatic bone disease has been widely studied by the interventional radiology community. To quote Deschamps and de Barre:

“The analgesic benefit of cementoplasty in bone metastases is well-documented in the medical literature as producing a reduction in pain in 80 to 97% of cases. This benefit is obtained irrespective of the bone site treated, whether vertebrae, long bones or flat bones. Alvarez et al. have shown that cementoplasty of a painful metastatic vertebra produced a significant reduction in pain in 81% of the patients treated (the mean VAS/10 progressing from 9.1 to 3.2) and the possibility of walking again in 77% of patients initially bedridden because of it. Cementoplasty is also very effective for metastatic pain of the long and flat bones, producing a significant improvement in the pain of 91% of patients (the mean VAS/10 progression from 8.7 to 1.9). This analgesic effect is obtained rapidly, generally between the first and third day following the procedure, permitting early postoperative mobilization of patients and a short hospital stay (24 – 48 hours). The physiological mechanisms of this analgesic effect can as yet be only hypothesized: the effect of the cement stabilizing microfractures and/or the effect of destruction of nociceptive fibers on contact with the cement, through the exothermic reaction generated during its polymerization. According to Urrutia et al., the mechanical effect takes precedence over the thermal effect since no histological lesions of intraosseous nerve fibers were seen on contact with cement injected into the vertebrae of rabbits. This seems to be confirmed by Anselmetti et al. who have found identical analgesic efficacy in three groups of patients treated with cements with very different peak polymerization temperatures (group A = 87 °C, group B = 60°C, group C = 45 °C).”

## **1.2 Rationale for Development of the IlluminOss Photodynamic Bone Stabilization System**

According to the Arbeitsgemeinschaft für Osteosynthesefragen/Association for the Study of Internal Fixation (AO) Foundation, there are four guiding principles for successful internal fixation of a fracture: the anatomical reduction of the fracture fragments; stable internal fixation of the bone; the preservation of blood supply; and the ability to facilitate early, active, pain free motion of the associated muscles and joints. These principles guided the development of the IlluminOss Photodynamic Bone Stabilization System (PBSS).

The IlluminOss PBSS may be uniquely suited to meet the needs of fracture fixation and overcome shortcomings of current solutions in pathological fractures by providing longitudinal stability along the length of the device, as with an IM nail, but via a minimally invasive delivery and stabilization technique. To place the device, a small incision is made to insert the device percutaneously into the medullary canal with minimal soft tissue dissection. The non-compliant balloon is then adjusted to span the fracture, and conforms to the patient's unique medullary canal, providing stable internal fixation once inflated with the monomeric cement. After the cement has been hardened by polymerization with visible light, additional hardware (pins and screws) may be used to stabilize the fracture. The location of supplemental hardware – such as pins and screws – is not pre-determined by the device configuration, as with traditional IM nails. This allows the surgeon to independently choose hardware placement, preserving blood supply to the bone, and optimizing the environment for normal biological healing to occur. Obstructive bracing is not required following implantation, and only a small surgical dressing is needed to dress the incision site. Thus, the patient is able to move the affected area following surgery and may potentially begin the return to the pre-fracture level of activity earlier than with traditional technology.

## **2      Intended Use & Device Description**

### **2.1    Intended Use**

The IlluminOss PBSS is indicated for use in fracture repair. It received CE Mark clearance in 2009 for use in the treatment of phalange of the hand, metacarpal, distal radius, radius, ulna, olecranon, clavicle, and fibula fractures. It provides stabilization for these fractures via a minimally invasive technique in which the bone is not subjected to significant weight bearing forces. As of June 2014, the PBSS has been used to treat over 400 bones in patients residing in Chile, United Kingdom, and the European Union. No intra-operative, post-operative, or systemic adverse device events have been reported. The PBSS is not cleared for use in the United States (US). More information regarding device use is provided in Section 3 of the protocol.

This study, conducted under an IDE from the U.S. Food and Drug Administration, will evaluate the use of the PBSS in the treatment of impending and actual pathological fractures of the humerus. The results of this study will be used to support a marketing clearance for the use of the PBSS for pathological fracture of the humerus in the United States.

### **2.2    Device Description**

The IlluminOss PBSS is manufactured by IlluminOss Medical, Inc. (East Providence, Rhode Island); the monomer cement is manufactured by Dymax Corporation (Torrington, CT, USA). The PBSS is comprised of an inflatable, thin walled polyethylene terephthalate (PET; DacronTM) balloon mounted on an insertion catheter. This balloon catheter system is designed to deliver the monomer cement to the fracture site via the medullary canal of the bone.

Once the balloon is in place and has spanned the impending or actual pathological fracture site, the delivery sheath is removed, uncovering the balloon; the balloon is then infused with light-curable monomer cement via a syringe, causing the balloon to expand. The inflated balloon circumferentially fills the medullary canal of the fracture, applying a transverse reduction force and stabilization to the fracture.

The bone is then visualized under fluoroscopy to ensure that the impending fracture or fracture site has been properly spanned and stabilized, with the balloon in the appropriate position, fully-inflated and contacting the inner diameter of the bone.

The light system is then activated, causing the photoinitiator in the monomer to rapidly polymerize and harden the cement *in situ*. The cured balloon thus becomes a bone stabilizing system (or “bone pin”) to aid in the support and healing of the bone fracture by primary callous formation and remodeling.

### **3 Justification for Clinical Investigation Design**

#### **3.1 Pre-Clinical Investigation Results**

The individual components of the PBSS and the hardened bone pin were tested under the conditions of the company’s ISO 13485:2003 compliant quality system, as well as domestic and international standards (MDD 93/42/EC-2007).

The liquid monomer, the disposable implant catheter set, and the polymeric bone pin have undergone extensive biocompatibility testing including genotoxicity, cytotoxicity, systemic sub-acute and sub-chronic toxicity, sensitivity and irritation testing, and implant performance evaluations. The pins were tested by an independent laboratory in pre-clinical models under GLP conditions of standard use and failure modes to assess the safety and performance of the implant materials. The results of the panel of testing indicated that the presence of the uncured monomer and cured polymeric bone pin were well-tolerated in animal models, had no negative effect on cell viability, and were not associated with permanent local or systemic complications.

The light source used to deliver visible light to the liquid monomer, the Blue Wave 75 VT Photodynamic Light Box, is similar to a commercially available product used in the UV adhesive industry. Testing of this component was conducted by an independent, certified testing agency, and evaluated all mechanical, electrical, software and user-interface functionalities in compliance with international standard IEC 60601-1, 2nd and 3rd Edition. A standard, commercially available 75-Watt light bulb is used within the unit to transmit light into the lumen of the catheter via a plastic light fiber. The safety and performance of the light output (wavelength and intensity spectrum) have passed all testing conducted by a second independent, certified testing agency.

#### **3.2 Prior Clinical Studies**

The PBSS has been cleared for use in the European Union (EU) for the treatment of phalanges of the hand, metacarpal, distal radius, radius, ulna, olecranon, clavicle, and fibula fractures. The ability of the device to perform its intended function in earlier indications is the rationale for performing this investigational study of the PBSS in impending and actual pathological fractures of the humerus secondary to metastatic malignancy.

##### **First-in-Man Study**

A First-in-Man feasibility study was conducted in Chile, South America for the use of the device in the treatment of phalange and metacarpal fractures. The study, “IlluminOss Medical Photodynamic Bone

Stabilization Study, Protocol #ILLUM-OUS-2008-001” enrolled 3 subjects from November 2008 until August 2009. Enrollment into the study closed in 2009 with no adverse device effects. Subjects met all inclusion/exclusion criteria and were treated for acute fractures of the metacarpal bone. Subjects returned to the hospital for Day 45, Day 90 and Day 180 follow-up visits. At each visit subjects were assessed for ADEs, clinical healing, and fracture alignment. The subjects completed a Disability of the Arm, Shoulder and Hand (DASH) questionnaire and radiographs were obtained. The Principal Investigator (PI) reported that all subjects were clinically healed by the Day 45 visit, and no local or systemic device-related complications were reported. The study is closed.

#### EU Registry Study

The EU Registry for the IlluminOss Bone Stabilization System, Protocol # ILLUM-EUREG-2010-001, was initiated in September 2010 and follow-up is ongoing. The aim of the registry is to collect technical and clinical outcomes on treated subjects. The subjects may be followed either until they are discharged from clinical care, or are followed for up to two years post index surgery. There are no pre-specified procedures or additional mandatory visits for subjects enrolled into the registry. Research personnel collect and enter standard of care demographic and fracture-related data, including radiographs, into a web-based database for review by IlluminOss personnel. The database prospectively queries for the incidence of adverse device effects.

Enrollment closed in January 2014. A total of 146 bones have been treated in 131 enrolled subjects at two centers in Germany and four centers in The Netherlands. The device has been used to treat acute fractures and has been used in revision surgeries across indications. It has been used alone, and with supplemental hardware, at the discretion of the surgeon.

Implant Location	TOTAL No. of Subjects Implanted
Metacarpal	14
Fibula	20
Humerus	42
humerus and femur	1
ulna	15
radius	1
distal radius	12
radius and ulna	2
distal radius and ulna	5

Pelvis	4
Tibia	1
tibia and fibula	3
Femur	7
Sternum	1
Unknown	3
Total # of subjects	131

Of the 131 subjects identified above, 23 subjects were available for a post-operative visit six months to two years or more post implant. Out of the 23 subjects, 70% (16/23) had radiographs taken, which were assessed by an independent assessor to evaluate maintenance of reduction, alignment, and radiographic healing. Twelve of the 16 subjects (75%) were treated for index fractures. Radiographic healing, as defined by cortical bridging and  $\geq 75\%$  dissolution of the fracture line, was reported for 92% (11/12) of the subjects. Four of the 16 subjects (25%) were treated with an IlluminOss device during a revision procedure. Radiographic healing, as defined above, was reported for 75% of the 16 subjects. No reports of device migration were reported for any subject at any visit. No unanticipated adverse device effects and no clinically significant adverse device effects have been reported.

## **4 Risks and Benefits**

### **4.1 Anticipated Clinical Benefits**

Compared to traditional impending fracture or fracture treatment technologies, subjects may benefit from participating in this study as use of the IlluminOss PBSS will likely result in: (1) shorter operative time; (2) shorter length of hospital stay; (3) fewer narcotic and physical therapy prescriptions; and (4) fewer post-operative complications. Additionally, subjects may benefit from regaining use of their limb earlier than if they were treated with conventional plates, IM rods, or cement alone. It is also possible that subjects may not experience any of these benefits. The results of this study will benefit the medical community treating actual and impending pathological fractures secondary to metastatic bone disease by evaluating the safety and performance of the PBSS.

### **4.2 Anticipated Adverse Device Effects (Risks)**

Adverse events (AEs) that may be anticipated in this clinical study are believed to be similar to and consistent with those associated with impending fractures, fractures, anesthesia, and surgical treatment, including the use of other commercially available plating and intramedullary fixation technologies. Complications may occur at any time during or after device implantation.

Possible risks that may be related to the IlluminOss device are believed to be similar to other types of bone pin devices. As with any IM fixation or plating system, possible risks may include, but are not limited to, the following:

- inability of the device to treat the fracture (maintain alignment and reduction);
- risk of implant fracture when used with screw fixation
- loosening, bending, cracking of the components or loss of fixation in bone;
- loss of anatomic position with non-union or malunion with rotation or angulation;
- the need for a second operation to treat the fracture or to remove the device;
- risk of uncured/cured monomer outside of the intended area, resulting in effects on the surrounding tissues and muscles, and in possible systemic side effects;
- relative increased risk of infection following a foreign body implant;
- x-ray findings of small bone loss (osteolysis) may be observed.

In addition, there is a rare chance that the balloon catheter may become damaged and leak the uncured monomer into the space of the fractured bone prior to the application of the light source to harden the monomer.

Complications associated with surgery and use of anesthesia are always possible, but are not common.

Possible risks of humerus surgery may include, but are not limited to, the following:

- infection;
- permanent numbness or weakness in the area of treatment;
- fractured bones do not heal together properly, or may heal with a bent shape;
- the need for a second procedure, not related to the investigational device
- abnormal bone loss or growth;
- swelling or bruising of tissue;
- thromboembolic event (blood clot or other material that could result in organ damage or failure);
- irregular heart rhythm;
- bleeding, possibly requiring transfusion;
- damage to nerves or blood vessels or muscles, or other tissue.

Possible risks of the use of anesthesia are:

- nausea and vomiting;
- headache;
- backache;
- sore throat or hoarseness;
- muscle soreness.

Other rare side effects or complications of the use of anesthesia include, but are not limited to:

- eye injury/blindness;

- lung complications;
- infection;
- damage to veins or arteries;
- damage to mouth, teeth or vocal chords;
- heart or blood pressure complications;
- brain damage;
- allergic reaction;
- prolonged recovery from anesthesia;
- seizure or stroke;
- nerve damage (including numbness, pain or paralysis);
- awareness or recall of the operation;
- death.

These events could possibly require surgery or other treatment to address the event.

#### **4.3 Residual Risks Associated With the Investigational Device**

There are no known residual risks associated with the use of the investigational device.

#### **4.4 Risks Associated With Participation in the Clinical Investigation**

Risks associated with participation in the investigation include additional radiographic assessments that may not be standard of care in the follow-up of traditional impending fracture treatment surgery. Enrolled subjects will have standard of care radiographs taken at the Day 7-14, 30, and Day 90 visits. Depending on the research site, the Day 180 and 360 radiographic assessments may not be considered standard of care. The risk of exposure to extra radiation at these time points is expected to be less than that received during a routine airplane flight.

#### **4.5 Risk Mitigation**

Risks will be minimized by ensuring that only board-certified orthopedic surgeons trained in the use of the IlluminOss PBSS participate as investigators in the study. Strict patient inclusion and exclusion criteria will be followed, enrolling only patients who meet criteria and provide written informed consent. During each follow up visit, subjects will be assessed for AEs, with particular attention to events that may be related to the surgical procedure and the investigational device. Medical monitoring will be conducted to review the frequency, severity, and relatedness of AEs. In addition, the study will be monitored to ensure compliance with the protocol and the continued acceptability of the investigator and institution.

#### **4.6 Risk to Benefit Rationale**

The potential benefits to enrolled subjects and the medical community outweigh the potential risks identified in this protocol. Robust preclinical testing has demonstrated the safety of the device components and all materials that come in contact with enrolled subjects. The early experience of the PBSS in CE Marked indications suggest the device is well tolerated and performs its primary function of

providing stabilization and alignment to fractured bones. This study has been designed to provide frequent safety assessments and to identify any potential new risks.

## **5 Study Objectives**

The primary objective of the study is to collect safety and performance data of the PBSS when used for the treatment of painful impending and actual fractures of the humerus secondary to metastatic malignancy.

## **6 Study Design**

This is a prospective, multi-center, open label study to evaluate the PBSS in the treatment of impending and actual pathological fractures of the humerus for the purposes of FDA marketing clearance.

A total of up to 80 subjects will be recruited from up to 20 sites in the United States .

### **6.1 Study Endpoints**

The following study endpoints will be evaluated in all subjects who consent to the study and are treated with the IlluminOss PBSS. All endpoints are subject-based unless otherwise specified.

#### **6.1.1 Primary Endpoint**

Pain Reduction

- Change in VAS Pain Score at Day 90

Functional Improvement

- Change in Revised Musculoskeletal Tumor Society Rating Scale for Upper Extremity (MSTS) at Day 90

Primary effectiveness will be evaluated relative to literature-based historical controls. These were selected on the basis of comparability to the target population and similarity to the investigational device. There are two primary effectiveness endpoints, reduction in pain at 90 days relative to pre-treatment baseline and improvement in function at 90 days relative to pre-treatment baseline. The changes in VAS pain and MSTS from pre-treatment baseline to day 90 will be involved in the primary effectiveness tests to be applied to enrolled patients who have actual or impending fractures, with VAS pain scores of at least 60mm. Non-inferiority of mean changes over time will be compared relative to reference values determined through evaluation of historical controls. Testing for VAS pain reduction will first be performed. Only if the null hypothesis of inferiority in mean VAS pain improvement is rejected at  $p<0.05$ , will the co-primary endpoint MSTS be similarly tested.

Safety Success is evaluated according to a composite endpoint by meeting all of the following criteria:

- Clinical
  - No Serious Device Related Complications
  - No additional surgical interventions:

- Revisions, supplements, fixations, or removals
- Radiographic
  - No device fracture, migrations, mal-alignment or loss of reduction or fixation

The number and percentage of patients achieving the Safety Success endpoint will be reported cumulatively for day 7-14, 30, and 90 and 180 and 360 and with 95% 2-sided exact binomial confidence intervals.

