### **6.1.2 Secondary Endpoints**

The secondary endpoints, evaluated at the Day 90 Visit, include:

- The individual components of the safety endpoint
- Other secondary endpoints include:
  - Duration of index procedure and length of hospital stay
  - Activities of Daily Living score through all follow-up intervals
  - Disability status
  - Evaluation of duration of physical therapy prescription
  - Assessment of prescription and over-the-counter analgesic medication use
  - Survivability from time of index procedure to death

The safety endpoints evaluated through Day 90 also include:

1. Incidence and number of AEs.
2. Incidence and number of procedure- and device-related complications.

The secondary endpoints and safety endpoints listed above will also be examined during the extended follow up portion of the trial at Day 180 and 360.

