## 13 Appendices

### 13.1 Study Definitions

#### A. Skeletal Definitions

**New or Recurrent Fracture:** Fracture of treated bone, confirmed via radiography or other imaging technique.

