#### G. Device Specific Definitions

**Clinically Significant Device Migration:** Change in bone pin position compared to immediate post-deployment position greater than 1cm (either proximal or distal) as documented by radiographic imaging and associated with clinical symptoms.

**Device Fracture:** Any loss of structural integrity (i.e. breakage or separation) of the implanted, polymerized bone pin. Documented by imaging or visually confirmed at the time of surgery or autopsy.

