6.7.1.1 Safety Success (Clinical and Radiographic)

Safety Success is evaluated according to a composite endpoint by meeting all of the following criteria:

- Clinical
 - No Serious Device Related Complications
 - No additional surgical interventions:
 - Revisions, supplements, fixations, or removals

If subject does not have device related SAE or no reoperation CRF page filled, he/she can be considered as clinical success, meeting both criteria: “No Serious Device Related Complications” and “No additional surgical interventions: Revisions, supplements, fixations, or removals”.

- Radiographic
 - No device fracture, migrations, mal-alignment or loss of reduction or fixation

If subject does not have device malfunction (fracture, migration, other) recorded on the CRF, subject can be considered as radiographic success, meeting radiographic criteria.

Subject achieves safety success if subject meets both clinical and radiographic success. The number and percentage of subjects achieving the safety success endpoint will be reported cumulatively at Day 7-14, Day 30, and Day 90, as well as at each of the extended follow up periods and with 95% 2-sided exact binomial confidence intervals. Only evaluable subjects will be included in the summary at each time point. Evaluable subject is defined as subject staying in the study long enough to reach the time point.

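### Safety Success has no component for fracture of the treated humerus, so an aligned, unoperated fracture around an intact pin can be scored a success

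*Protocol*

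**What the plan says.** Protocol 6.1.1, under the primary endpoint heading, defines Safety Success as a composite in which every criterion must be met. The clinical criteria are "No Serious Device Related Complications" and no additional surgical intervention, listed as "Revisions, supplements, fixations, or removals". The radiographic criterion is "No device fracture, migrations, mal-alignment or loss of reduction or fixation". The synopsis repeats this. The result is a count and percentage at each follow-up time, with an exact 95% interval. There is no hypothesis, threshold or assumed rate.

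Protocol 13.1 separates two kinds of fracture. Device Fracture (13.1 G) is "Any loss of structural integrity (i.e. breakage or separation) of the implanted, polymerized bone pin". New or Recurrent Fracture (13.1 A) is "Fracture of treated bone, confirmed via radiography or other imaging technique". Only the first enters the composite.

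SAP 6.7.1.1 codes the radiographic part from the case report form: "If subject does not have device malfunction (fracture, migration, other) recorded on the CRF, subject can be considered as radiographic success". Protocol 6.1.2 makes "The individual components of the safety endpoint" a secondary endpoint, but a bone fracture is not one of those components. SAP 6.7.1.1 specifies a summary of the composite only.

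**The concern.** An impending fracture is stabilised because the bone may break. In that group, prior fracture of the site is an exclusion (Protocol 6.4.1, exclusion 12), so a later fracture of the humerus is a clear new event and is directly relevant to how the device performs. A composite that looks at the pin, its alignment and any reoperation, but not at the bone, can record success in a subject whose treated bone has broken. The rate sits under the primary endpoint heading of a study intended to support US marketing clearance, so a reader may take it to cover this event.

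**Working it through.** No figure in the plan depends on this point, so there is none to reproduce. The check is to take one case through each criterion: an impending fracture that later completes, with the pin intact and the bone aligned, managed without surgery.

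| Criterion | Source | Does it catch this case? |
|---|---|---|
| Device fracture | Protocol 6.1.1, 13.1 G | No. The definition concerns the pin. |
| Migration | Protocol 6.1.1 | No. The pin has not moved. |
| Mal-alignment, loss of reduction or fixation | Protocol 6.1.1 | No, while the bone stays aligned and fixed. Yes if it displaces. |
| Additional surgery | Protocol 6.1.1, 13.1 G | No, if none is done. Splints and casts are expressly not supplemental fixation. |
| Serious device-related complication | Protocol 6.1.1, 9.1, 9.2 | Only if the event is both serious and rated device-related. |
| Device malfunction on the form | SAP 6.7.1.1 | Only if a site enters it under the residual category. |

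The attribution row needs care. Protocol 9.1 calls an event device-related when concurrent disease is an unlikely explanation. Every subject has metastatic disease at the site, so progression is always an available explanation. Protocol 9.2, however, allows a rating of possibly related even when another cause is at least as likely. Attribution to tumour therefore does not force the event out of the composite, but it makes that route uncertain.

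**Illustration of size.** The inputs are n = 80 (Protocol 6.4.5), an assumed impending share s, and an assumed rate q at which those bones break after fixation. Neither s nor q is in the documents. The number of fractures is k = 80 × s × q.

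- s = 0.50: 80 × 0.50 × 0.05 = 2, and 80 × 0.50 × 0.15 = 6.
- Wider range: 80 × 0.25 × 0.05 = 1, and 80 × 0.75 × 0.15 = 9.

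The exact (Clopper-Pearson) 95% limits for x successes are the 2.5% quantile of Beta(x, n − x + 1) and the 97.5% quantile of Beta(x + 1, n − x). At x = n the upper limit is 100%. Suppose there are no other failures and every one of the k fractures is missed. The reported rate is then 80/80 = 100% (95.5-100). Counting the fractures would give:

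| k | Rate | Exact 95% CI |
|---|---|---|
| 1 | 79/80 = 98.8% | 93.2-100.0 |
| 2 | 78/80 = 97.5% | 91.3-99.7 |
| 4 | 76/80 = 95.0% | 87.7-98.6 |
| 6 | 74/80 = 92.5% | 84.4-97.2 |
| 9 | 71/80 = 88.8% | 79.7-94.7 |

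For given s and q these are ceilings, because a fracture is missed only if it stays aligned, is not reoperated and is not rated a serious device-related event. If a quarter met all three conditions (a further assumption), the 2 to 6 would become 0.5 to 1.5.

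**The case against.** A reader might infer that any fracture completing around an intact pin is scored a success. The documents do not support that. Displacement fails the Protocol criterion on alignment, reduction or fixation. Revision, removal or added fixation fails the surgical criterion, and the SAP looks for a completed reoperation page. A serious event attributed to the device fails too.

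Nor is the event hidden. Adverse event incidence is a named safety endpoint (Protocol 6.1.2). SAP 6.7.1.2 tabulates events cumulatively to Days 90, 180 and 360, with further tables by seriousness, severity and relatedness, and lists them all. In those tables possibly related events count as related, and under SAP 7.0 a missing relationship does as well. Appendix 13.1 is largely a glossary of adverse events, so a term defined there but absent from the composite is not in itself proof of oversight.

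A reader might also take the 15% fracture figure for a Mirels score of 8 (Protocol 1.1) as the expected rate here. It comes from the background on deciding whether to fix a bone and is not a rate after stabilisation. The case report form and any imaging charter are not available, so how sites or the core imaging service would record a bone fracture is unknown.

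All of this stands, and it limits the size of the problem. It does not supply the missing component: an adverse event row does not change how the subject is scored in Safety Success.

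SAP 6.7.1.1 also names no explicit data source for mal-alignment or loss of reduction. That is a separate discrepancy, and this point does not rely on it.

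**Conclusion.** The omission is real and follows from the text alone. It affects a narrow case: a fracture of the treated humerus that stays aligned around an intact pin, leads to no counted surgery and is not rated a serious device-related complication. That subject is scored a success in both documents, unless a site happens to enter the event as another kind of device malfunction.

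It would be too strong to conclude that the trial's success decision is at risk. Formal success rests on VAS and MSTS, and Safety Success is descriptive, so no test, alpha or sample size changes. The number of subjects affected cannot be estimated from the documents. The 2 to 6 in 80 is an illustrative ceiling that rests on an assumed 50% impending share and an assumed 5-15% fracture rate. This is a cheap improvement worth making, not a defect that must be repaired before the trial can be interpreted.

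**What to change.** - In Protocol 6.1.1, the synopsis and SAP 6.7.1.1, add absence of a new fracture of the treated humerus (as defined in 13.1 A) to the radiographic criteria.
- Score it from the radiographs already scheduled at every follow-up visit (Protocol 8.3 and 13.2), and name the data source in the SAP.
- For subjects enrolled with an actual fracture, count only a fracture distinct from the index fracture, so that persistence of the index fracture is not a failure.
- Report it as its own row with an exact 95% interval, separately for impending and actual fractures.
- Make the change before database lock, so that the composite is not altered after results are seen.

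The cost is wording in two documents and one table row. No procedure is added. The downside is that the Safety Success rate may be slightly less favourable.
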